3.4.2. Impact evaluation of enhanced RACD

3.4.2.1. Study design

This study will employ a two-arm cluster-randomized control trial design with randomization of clusters into either RACD or control.

3.4.2.2. Randomization

A total of 32 health center catchment areas (HCCAs) in Laos will be selected for inclusion based upon incidence per 1000 population between October 2017 and September 2018. HCCAs with higher incidence will be prioritized to improve power; where possible, directly neighboring HCCAs will not both be included to reduce contamination. Restricted randomization of the HCCAs into either RACD or control arms will be conducted, whereby sets of randomizations (with 16 HCCAs in each arm) will be generated that achieve balance across arms on incidence per 1,000 over the prior year, population size, and amount of forest cover. From these sets of potential randomizations, a single randomization will be randomly selected to assign 16 HCCAs each to the RACD or control group. Restricted randomization in this way will ensure balance across intervention and control groups on potential confounding factors. The 'sample' command in Stata v14 (StataCorp, College Station, TX) will be used to implement randomization.

Table 5. Study arms

Study arm	Description	Lao PDR
RACD	Reactive case detection led by VMWs in response to cases in study area HCCA, with follow up testing with HS-RDTs/RDTs in both villages and forest workers; referrals for qualitative G6PD testing for P. vivax cases and 14-day PQ for G6PD non-deficient	16
Control	Standard of care including case management through health facilities and malaria posts/VMWs; village-based RACD conducted by district staff in some areas	16

3.4.2.3. Primary outcome measures

1. Confirmed *P. falciparum* and *P. vivax* malaria parasite incidence: defined as the number of OPD malaria confirmed and suspected cases per person per year for each HCCA, as ascertained from the health facility registers, utilizing administrative catchment population size estimates for the exposure denominator.
2. PCR-based *P. falciparum* and *P. vivax* parasite prevalence in sampled HCCAs: defined as the proportion of individuals ≥ 18 months old with *P. falciparum* or *P. vivax* infection (detected by PCR) out of all individuals ≥ 18 months tested within the endline survey (2020).
3. HS-RDT/RDT -based test positivity rate in village and forest-based reactive case detection: defined as the proportion of all individuals tested by HS-RDT/RDT in response to an index cases, with a positive HS-RDT/RDT, among the population older than 18 months.

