
[name] [name] Assistant [name] of Biostatistics and Epidemiology School of Public Health and Health Sciences University of Massachusetts – Amherst [contact]
	
[name] Independent consultant [contact]
	
[name] Assistant [name] School of Public Health and Tropical Medicine [contact]

[name], MA Assistant [name] of Medicine / Div. of Infectious Diseases University of California, San Francisco [contact]
		

1 Protocol summary

Aim	To determine the effectiveness and feasibility of enhanced reactive case detection (RACD) targeting high-risk villages and forest workers for reducing Plasmodium falciparum and Plasmodium vivax transmission in southern Lao PDR
Primary research question and hypothesis	
1. Null hypothesis: Compared to standard of care, which includes case management and RACD with conventional RDTs and is directed at villagers, there is no additional benefit of enhanced community-based RACD, which is conducted by village malaria workers (VMWs), uses HS-RDTs, and targets forest workers in addition to villagers, for reducing P. falciparum and P. vivax confirmed case incidence and parasite prevalence over an 18-month period in Lao PDR.
 
Research hypothesis: Enhanced community-based RACD will be more effective than standard of care case management and RACD at reducing P. falciparum and P. vivax confirmed case incidence and parasite prevalence over an 18-month period in Lao PDR.

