Estimated enrollment	
 1) Confirmed case incidence across 32 health center catchment areas: population of approximately 145,000 2) Village-based reactive case detection: estimated 14,400 3) Forest worker reactive case detection: estimated 2,880 4) Endline household survey: 14,080 persons at end-line 5) Qualitative surveys: 6 Focus group discussions (FGDs) and 18 Key informant interviews (KIIs) at baseline, 9 FGDs and 18 KIIs at end-line. 6) Competency checklists with 32 VMWs at baseline, midline, and endline 7) Entomological human landing catches: 20 collectors over three nights at baseline
Statistical and analytical plan	Rapid reporting of microscopy or RDT and HS-RDT positivity will be analyzed as interventions are implemented (or shortly thereafter) to provide preliminary assessment of interventions. Negative binomial (for incidence) and generalized linear mixed effects (for prevalence) models will be used to test the effect of each intervention independently (main effects) relative to control (standard of care). For the enhanced RACD vs. control comparison, both country-specific and pooled analyses will be conducted.

2 Background and introduction

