2.5. Study overview

To test this hypothesis, this study will employ a cluster randomized controlled trial design with two comparison arms:

1. **Control:** standard of care - passive case management provided through community-based VMWs and existing health facilities; includes village-based RACD with conventional RDTs conducted by district surveillance teams.
2. **Enhanced community-based RACD:** RACD conducted by community-based VMWs using both HS-RDTs and conventional RDTs within villages and among forest workers.

The primary outcome measures to assess effectiveness include *P. falciparum* and *P. vivax* confirmed case incidence over the study period; PCR-based *P. falciparum* and *P. vivax* prevalence at endline; and HS-RDT test positivity rate in village and forest worker RACD. Secondary outcomes measures will examine the operational feasibility, safety, and acceptability of VMW-led reactive approaches and G6PD testing, referral to district or provincial-level facilities, safety and treatment adherence for *P. vivax* cases. The trial will be implemented between June 2019 and December 2020 in Lao PDR. The primary evaluation will be conducted following an end-line cross-sectional survey in November/December 2020.

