3.3. Interventions

Each intervention cluster (i.e., health facility catchment area) will be randomly assigned to either the RACD intervention or control arm (in a 1:1 ratio) before the study begins. The randomization process is described in more detail in section 3.4.2.2 below. Interventions (RACD) will be conducted by VMWs and/or community volunteers in response to an index case (presenting to VMW, malaria post, health facility, or other testing facilities) occurring anywhere within a selected intervention health facility catchment area. At presentation, all index cases will initially be asked about recent forest exposure. The intervention response for cases with no history of forest exposure in the past two months will be conducted only at the village level, while the response for cases with history of recent forest exposure will include both village and forest-worker populations. Forest-worker RACD will be conducted at recent work sites if accessible and located within the health facility catchment and/or amongst peer forest-goers referred by the index case. VMWs in intervention villages will maintain a register of forest workers and locations to assist them with tracking. In Lao PDR, health center staff will assist with RACD during the first six months of the study only, after which point VMWs will operate independently.

Index case capture

Interventions will be initiated after an individual from a cluster assigned to an intervention is diagnosed with malaria and notified to the study team. Suspected malaria cases attending local health services (hospital, health center, health post, or VMW) will be tested with an RDT or microscopy according to routine practice. All cases parasitologically confirmed by RDT will be treated according to national guidelines and asked for informed consent to participate in the study. If the patient gives informed consent, the VMW or health staff will promptly notify the study team using mobile phone. A short screening questionnaire will be administered to determine location of residence and recent forest or other travel. Additionally, finger prick blood will be collected on DBS from the index case for subsequent analyses.

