In the event that household members are not present at the time of testing, the VMW will ask if any absent household member has been ill with fever during the previous two weeks. If any absent household members are reported as having recent fever history or if any other household members test positive for malaria, the VMW will schedule a time to revisit the household. At this time, the VMW will administer the informed consent form to any previously absent household members and then test these individuals (and treat positive cases). Febrile individuals testing negative by RDT(s) will be referred to the nearest health center.

RACD of cases' co-workers/co-travelers

Index cases will be screened by the VMW at their households at the time of case investigation to determine if they have traveled or worked in a forest or forest-fringe area within the past 30 days. If eligible, the case will trigger two reactive recruitment strategies to screen and treat others who recently traveled or worked with the case in a forest or forest-fringe location:

1. *Peer-referral RACD (PR-RACD)*: In this strategy, the case will identify specific co-travelers or co-workers resident in their village who had spent the night with the case at a forest or forest-fringe area and spent the night there in the past 30 days.
2. *Venue-based RACD (VB-RACD)*: In this strategy, co-workers will be recruited directly from (accessible) forest or forest-fringe work sites where the index case worked and spent at least one night in the past 30 days.

Participating index cases who meet eligibility criteria will be asked to provide a list of all people who have worked or traveled in the forest or forest-fringe with him/her in the past 30 days between dusk and dawn and their contact information (names, phone numbers, home addresses) (peer-referrals). The questionnaire will elicit from index case all forest and forest-fringe work sites where the case has spent the night in the past 30 days, as well as contact information for any respective employers.

For PR-RACD, VMWs will contact peer-referrals by phone, at their home, or through village leaders and invite them to participate in a survey interview and malaria testing at a time and place that is most convenient. This may be the referral's place of residence, a health facility, or another location in the village that provides sufficient confidentiality, such as a coffee shop.

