3.4. Study evaluation methods

3.4.1. Overview of evaluation activities by study objectives, outcomes, and data collection activities

Table 4. Overview of evaluation activities

Study activity	Research objective	Primary outcome measures	Data collection activity
Activity 1: Impact evaluation of enhanced RACD	1. Evaluate the relative effectiveness of enhanced community-based RACD using HS-	Total confirmed outpatient (OPD) P. falciparum and P. vivax malaria case incidence among all ages by health facility catchment	Routine malaria data from all reporting VMWs, health centers and district hospitals

	RDTs in villages and forest-based HRPs, compared to control	P. falciparum and P. vivax prevalence in all individuals	Cross-sectional parasite survey November-December 2020	
		HS-RDT and RDT test positivity rate	HS-RDT and RDT positivity data from RACD intervention data	
Activity 2: Assessment of the feasibility and acceptability of community-based RACD	1. Assess the operational feasibility of community-based RACD	Population coverage of RACD and interventions	RACD intervention data	
		Proportion of VMWs who rate conducting the RACD interventions as very easy, somewhat easy, somewhat difficult, and very difficult, and changes in proportions over time	Entrance, mid-intervention, and exit competency checklists with VMWs; focus group discussion and interviews with VMWs at end-line	
		Costs of RACD as unit and total costs; cost-effectiveness will be assessed as an incremental cost effectiveness ratio (ICER)	Program data on costs combined with estimates of program effectiveness	
	2. Assess the acceptability of community-based RACD	Proportion of targeted individuals refusing RACD intervention	RACD intervention data	
		Proportion of survey respondents who strongly disagree, disagree, are ambivalent, agree and strongly agree on the importance and acceptability of community-based RACD	Cross-sectional survey and qualitative studies at endline with villagers, forest workers, VMWs and other health sector staff	

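### Primary outcome 1 is titled confirmed incidence, but its definition also counts suspected cases, against every other passage that names the case type

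*Protocol*

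**What the plan says.** Item 1 of Protocol section 3.4.2.3 carries a title restricting it to confirmed *P. falciparum* and *P. vivax* incidence. The definition under that title is "defined as the number of OPD malaria confirmed and suspected cases per person per year for each HCCA", taken from the health facility registers.

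The other places that name a case type for this outcome all say confirmed:

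- Section 1 (hypotheses) and section 2.4: "confirmed case incidence and parasite prevalence over an 18-month period in Lao PDR".
- Section 1 (estimated enrollment): "Confirmed case incidence across 32 health center catchment areas".
- Section 2.5: "confirmed case incidence over the study period".
- Section 3.4.1, evaluation table, Activity 1: "Total confirmed outpatient (OPD"), for both species and all ages.
- Section 3.4.2.4.1: the heading of the incidence sample-size section.
- Section 3.4.2.5.1: both the heading and the description of what the reporting units supply.
- Section 3.4.2.6, Outcome 1: the regression is fitted to cumulative counts of confirmed cases.

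The list of primary outcomes in section 1 and the body text of section 3.4.2.4.1 name no case type. No other passage counts suspected cases in this outcome.

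Section 3.3 (index case capture) shows how the protocol uses the two words. First: "Suspected malaria cases attending local health services (hospital, health center, health post, or VMW) will be tested with an RDT or microscopy". Then: "All cases parasitologically confirmed by RDT will be treated according to national guidelines".

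**The concern.** The title and the definition of one primary outcome give two different numerators, and in this protocol the two words are not synonyms. Suspected describes a patient before the test; confirmed describes a patient after a positive one. On that usage the defined numerator includes people who turn out not to have malaria. They also have no species result, although the outcome is specific to *P. falciparum* and *P. vivax*.

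Enhanced reactive case detection has no reason to reduce the number of test-negative patients. Counting them adds a component without a treatment effect to both arms, and the rate ratio moves toward 1.

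The addition might also differ between arms. Under household reactive case detection in section 3.3.1, "Febrile individuals testing negative by RDT(s) will be referred to the nearest health center". Those referrals could raise suspected counts at intervention facilities in particular. The protocol gives no fever rate among contacts, and Table 5 says that district staff also conduct village reactive case detection in some control areas, so the size of this route is unknown.

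**Working it through.** **Step 1: comparing the passages.** Nine places name the case type for this outcome: sections 1 (hypotheses), 1 (enrollment), 2.4, 2.5, 3.4.1, 3.4.2.4.1 (heading), 3.4.2.5.1, 3.4.2.6 and the title of item 1 in 3.4.2.3. All nine say confirmed. The definition under that title is the only text that adds suspected cases. This alone establishes the contradiction; no figure is needed.

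**Step 2: what the definition would do if followed.** The protocol states no suspected-case rate, so this is an illustration under assumed values.

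Inputs from section 3.4.2.4.1: 2.5 cases per 1000 per year (taken here as the control-arm rate), 4000 people per catchment, 18 months (1.5 years), 50% reduction.

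- Control catchment: 2.5/1000 × 4000 × 1.5 = 15.0 confirmed cases.
- Intervention catchment: 15.0 × 0.5 = 7.5 confirmed cases.
- Ratio on confirmed cases: 7.5/15.0 = 0.50.

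Let *e* be the number of test-negative suspected patients per catchment over 18 months, assumed equal in both arms and unaffected by the intervention. The ratio on the combined count is (7.5 + *e*)/(15 + *e*).

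| *e* per catchment | per month (*e*/18) | combined ratio | apparent reduction |
|---|---|---|---|
| 0 | 0 | 7.5/15 = 0.50 | 50% |
| 7.5 | 0.4 | 15/22.5 = 0.67 | 33% |
| 15 | 0.8 | 22.5/30 = 0.75 | 25% |
| 75 | 4.2 | 82.5/90 = 0.92 | 8% |

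**Step 3: the same at the Table 1 rate.** Table 1 (section 3.1) gives 6.77 cases per 1000 and 147,798 people in 32 catchments.

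- Control catchment: 6.77/1000 × 147,798/32 × 1.5 = 46.9 confirmed cases.

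With *s* test-negative patients per confirmed control case, the ratio is (0.5 + *s*)/(1 + *s*). The three diluted rows above are *s* = 0.5, 1 and 5, so the ratios are the same by construction. What changes is the number of patients needed:

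| *s* | added per catchment (46.9 × *s*) | per month | combined ratio |
|---|---|---|---|
| 0.5 | 23.5 | 1.3 | 0.67 |
| 1 | 46.9 | 2.6 | 0.75 |
| 5 | 234.5 | 13.0 | 0.92 |

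The direction holds for any *e* above zero. The size depends entirely on *e*, which the protocol does not supply. The referral route in section 3.3.1 is not in these figures, since they assume equal addition in both arms.

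**The case against.** The strongest reply is that this is a two-word drafting slip which the protocol itself resolves. The item's own title says confirmed, a suspected case cannot have a parasite species, and the analysis section models confirmed counts. On this view a competent analyst would never count suspected cases. That describes the likely intent correctly, and it makes the harm conditional. It does not remove the error: section 3.4.2.3 is the formal definition of the outcome, nothing in the protocol ranks section 3.4.2.6 above it, and section 5.4 says the protocol will be filed on a public registry.

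A second reply is that suspected might mean untested patients diagnosed clinically, perhaps a small group, since section 3.3 says suspected cases are tested as a matter of routine. Section 3.3 indeed does not say how a register labels a patient after a negative test. The dilution figures apply only to the test-negative reading. But an untested case is not confirmed either, so the contradiction stands on both readings.

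Third, the ratios rest on assumed patient numbers, and repeating them at the Table 1 rate adds no independent evidence. This stands: they show direction and sensitivity, not an expected bias. The referral route is likewise only a possibility.

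Finally, the definition draws on health facility registers, while sections 3.4.1 and 3.4.2.5.1 list further reporting units. Correcting the case type does not settle that; it is a separate matter.

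**Conclusion.** The concern holds. The definition of primary outcome 1 contradicts its own title and every other passage that names the case type. As written, it would admit patients without parasitological confirmation.

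The consequence is conditional on someone following section 3.4.2.3 rather than section 3.4.2.6. In that event a true ratio of 0.50 would appear as 0.67 to 0.92 in the illustrated range, which corresponds to about 0.4 to 4.2 test-negative patients per catchment per month with the sample-size inputs, or 1.3 to 13.0 at the Table 1 rate. These figures assume equal numbers added in both arms, no intervention effect on them, and the test-negative reading of suspected. This should be fixed because it is the definition of a primary outcome, although the intended numerator is clear from the rest of the protocol.

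**What to change.** In item 1 of section 3.4.2.3, delete *and suspected*, so that the numerator is confirmed cases per person per year for each catchment. That brings the definition into line with its title, the evaluation table in section 3.4.1 and the analysis in section 3.4.2.6. For full clarity, the sentence could also state that confirmed means positive by RDT or microscopy for *P. falciparum* or *P. vivax*; the deletion alone is enough to remove the contradiction.

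The cost is two words in one sentence. Data collection, sample size and the regression model do not change.

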3.4.2.4. Sample size

3.4.2.4.1. Confirmed *P. falciparum* and *P. vivax* malaria parasite incidence

Assuming an average baseline transmission of 2.5 per 1000 population per year (all species, from 2017 health system data across study sites and a 50% reduction), an average population of 4000 per health facility catchment, and coefficient of variation of 0.6 (based upon 2017 health system data), in order to detect a 50% reduction in cumulative infection incidence (as measured by routine health system surveillance data over an 18-month period) in a random effects Poisson or negative binomial model, a minimum of 16 randomization units will be required in each study arm. A total of 32 health facility catchment areas will be included in Lao PDR, with 16 allocated each to enhanced RACD and control.

Only health facility catchment areas with at least 3 malaria cases in the past year will be considered for inclusion.

3.4.2.4.2. Population-level *P. falciparum* and *P. vivax* malaria parasite prevalence

Assuming 16 health catchment areas per arm, a baseline control prevalence by qPCR (all species) of 2.5%, and a coefficient of variation of 0.5, a minimum of 400 individuals per catchment area will be required in order to detect a 50% reduction in prevalence at endline. Assuming a 10% refusal rate, a total of 14,080 individuals will be required across both arms at the end-line survey. Assuming 4 individuals per household, this will result in a total of 3,520 households sampled, or 110 per health facility catchment area.

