3.4.2.5.2. Cross-sectional surveys

An endline survey will be conducted in November/December 2020 to obtain an unbiased estimate of *P. falciparum* and *P. vivax* malaria parasite prevalence in each study arm, as well as assess intervention coverage, treatment seeking, and mobility and forest going activities. The endline survey will include testing with HS-RDTs/RDTs and collection of DBS for qPCR-based testing.

Sampling frame and sampling strategy

Within each of the HCCAs selected for study inclusion, survey staff will work with village authorities to update household ledgers, and then all households will be enumerated and a GPS point captured. All households will be given a study ID card and household sticker with a unique barcode, which will be used throughout the study to identify repeat visits at each household, as well as for individuals to present at health facilities if they report for care.

In order to reduce potential contamination due to proximity to intervention areas (for the control arm), households within 2 km of a neighboring study village will be removed from the sampling frame. Households will be selected via simple random sampling from the remaining HH lists.

Questionnaires and human specimen collection

During the endline survey, selected households will be visited and the head of household interviewed by a study staff member using a tablet or paper form. To capture any household members not present at time of survey, study staff will plan for an overnight stay whenever feasible to schedule visits for early morning or late evening, but will have a maximum of four visits to each HH. The survey questionnaire used for interviewing will be developed in English with input from local health staff. This

will then be translated to Lao, and back-translated by a fluent bilingual health expert prior to field testing.

The survey questionnaire will capture household-level demographics, and assess potential risk factors for malaria infection. Information collected will include age, gender, pregnancy, nationality, ethnicity, occupation, socioeconomic status, travel history, history of malaria, treatment seeking for fever in the past two weeks, individual and household use of vector control measures, housing structure type, proximity to forest and forest-fringe, and frequency of overnight sleeping in forest or forest-fringe areas.

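### The endline survey total of 14,080 yields about 396 tested per catchment at the assumed 10% refusal, 1% below the protocol's own minimum of 400; separately, the calculation shows no allowance for testing whole households

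*Protocol*

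**What the plan says.** Section 3.4.2.4.2 of the protocol sizes the endline survey for qPCR prevalence, one of the primary outcomes listed in section 3.4.2.3. Its inputs are:

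- clusters: "Assuming 16 health catchment areas per arm";
- control prevalence: "a baseline control prevalence by qPCR (all species) of 2.5" (per cent);
- between-catchment variation: "a coefficient of variation of 0.5";
- requirement: "a minimum of 400 individuals per catchment area will be required in order to detect a 50% reduction in prevalence at endline".

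It then allows for refusal ("Assuming a 10% refusal rate, a total of 14,080 individuals will be required across both arms at the end-line survey") and converts people to households: "Assuming 4 individuals per household, this will result in a total of 3,520 households sampled, or 110 per health facility catchment area".

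The total recurs under Estimated enrollment in the Protocol summary ("Endline household survey: 14,080 persons at end-line"), and the 3,520 households recur in section 3.4.3.3 as the base for the acceptability data. On sampling, section 3.4.2.5.2 says: "Households will be selected via simple random sampling from the remaining HH lists". The same section invites all members aged 18 months or older, residents and visitors alike, to be tested. The prevalence model in section 3.4.2.6 names random intercepts for health center catchments only.

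**The concern.** There are two separate points.

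**Refusal.** A requirement for people tested is converted to people approached by dividing by the expected participation, here 0.9. Multiplying by 1.1 falls slightly short. Because the protocol calls 400 a minimum, its own total should deliver 400 at its own refusal rate.

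**Households.** People in one household share exposure, so four members can carry less information than four people drawn separately from the catchment. The inputs listed for the 400 describe variation between catchments and nothing below that level. Prevalence is measured at endline only, so no baseline survey is available to recover lost precision. If the design sits close to its power target, a modest household correlation could take it below.

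**Working it through.** **1. Reproducing the stated total**

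- Tested people required: 32 × 400 = 12,800.
- 12,800 × 1.1 = 14,080, the stated figure exactly.
- 14,080 / 4 = 3,520 households; 3,520 / 32 = 110 per catchment. Both match.

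**2. What that total yields at 10% refusal**

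- Approached per catchment: 14,080 / 32 = 440.
- Tested: 440 × 0.9 = 396 per catchment, 12,672 overall.
- Shortfall against 400: 4 per catchment, or 1%.
- Correct inflation: 12,800 / 0.9 = 14,223, which is 143 more than stated (1.0%).
- In whole households: 111 × 4 × 0.9 = 399.6, still short; 112 × 4 × 0.9 = 403.2. So 112 per catchment, 3,584 households, 14,336 people.

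**3. Reproducing 16 × 400**

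The section gives no alpha, sidedness, power or formula. Assume two-sided 0.05, 80% power and the standard formula for proportions with coefficient of variation k:

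c = 1 + (z_α + z_β)² × [p0(1 − p0)/m + p1(1 − p1)/m + k²(p0² + p1²)] / (p0 − p1)²

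with p0 = 0.025, p1 = 0.0125 (a 50% reduction), k = 0.5 and m = 400:

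- Sampling term: (0.024375 + 0.01234375) / 400 = 0.0000918.
- Between-catchment term: 0.25 × (0.000625 + 0.00015625) = 0.0001953.
- (p0 − p1)² = 0.00015625; (1.96 + 0.84)² = 7.849, using unrounded z values.
- c = 1 + 7.849 × 0.0002871 / 0.00015625 = 15.4, which rounds up to 16 per arm.

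Power at 16 per arm is 81.5% with 400 tested and 81.4% with 396. For exactly 80% the formula needs about 356 per catchment, so 400 has about 12% slack. No household term was needed to reach 16 × 400. Other targets fit less well: two-sided 90% needs 20.3 clusters per arm, one-sided 0.05 needs 12.4 at 80% and 16.7 at 90%.

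**4. Adding a household design effect**

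Multiply the sampling term by 1 + (s − 1) × ICC, where s is the number tested per household. If whole households refuse, s stays at 4 (design effect 1 + 3 × ICC). If individuals refuse, s is 4 × 0.9 = 3.6 (design effect 1 + 2.6 × ICC). The protocol gives no ICC, so the values below are assumed.

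| Household ICC | Power at 396 tested, s = 4 | Power at 396 tested, s = 3.6 |
|---|---|---|
| 0 | 81.4% | 81.4% |
| 0.05 | 79.6% | 79.8% |
| 0.10 | 77.8% | 78.2% |
| 0.20 | 74.3% | 75.2% |

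Break-even for 80%: the design effect may reach 396 / 355.5 = 1.11. That is an ICC of 0.114 / 3 = 0.038 for s = 4, or 0.114 / 2.6 = 0.044 for s = 3.6, so about 0.04 either way.

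**The case against.** **The refusal slip is immaterial.** This stands as to size. It is 143 people in 14,080, and 396 tested still exceeds the 356 that suffice for 80% power. Four per household is itself a round planning figure: at 4.04 per household, 110 × 4.04 × 0.9 already gives 400. A reader might infer that the primary-outcome sample size is wrong in a way that endangers the trial; the documents do not support that. What remains is that the stated total misses a floor the protocol itself calls a minimum.

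**Household correlation does not reduce the number tested.** This also stands. A reader might infer that sampling households is a further reason why the plan misses 400 people per catchment. It is not: only the refusal arithmetic does that. Household correlation lowers the information those people carry.

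**The protocol nowhere says that household members are independent.** Correct. That reading is an inference from the absence of any household term and from the fact that 16 × 400 is reproduced without one. The slack in 400 could cover a small design effect, up to an ICC of about 0.04, and the section gives no source for the 0.5. But nothing says that either was meant as a household allowance.

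**The power loss rests on assumed values.** It does: alpha, the power target, the formula and the ICC are all supplied here. The table is therefore a sensitivity range and does not show that the survey is underpowered. Further detail may also sit in an analysis plan that is not available. The sample-size calculation itself, however, is fixed in the protocol.

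**Conclusion.** Both points hold, and both are minor as they stand.

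The refusal point needs no outside assumption. At the protocol's own 10%, 14,080 approached yields about 396 tested per catchment, 1% under its minimum, at a cost of about 0.1 percentage point of power.

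The household point is an unstated assumption that should be justified, not an arithmetic error. Under the assumptions in the working, power is 81.4% at 396 tested with no household correlation. It falls below 80% above an ICC of about 0.04, to about 78% at 0.1 and 74–75% at 0.2. The ranges cover 4 and 3.6 tested per household. If the true household ICC is about 0.04 or less, the 80% target is still met.

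**What to change.** 1. In section 3.4.2.4.2, either state that 14,080 approached yields about 396 tested per catchment at 10% refusal, or correct the target to 14,223 people. In whole households the latter is 112 per catchment, 3,584 households and 14,336 people. Carry the choice into Estimated enrollment in the Protocol summary and into section 3.4.3.3.
2. State the alpha, sidedness, power and formula behind the 400. Add a household design effect, saying whether refusal is expected by person or by household, and restate the power or the detectable reduction over a stated ICC range such as 0.05 to 0.2.

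The cost is a few restated figures or, if the target is corrected, two more households per catchment (64 in all). The second step asks for disclosure and does not require more enrolment.
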